7.5 SAFETY

7.5.1 ADVERSE EVENTS

All AEs that occur during the study or continue after enrollment into this study will be recorded and classified on the basis of MedDRA terminology. Treatment-emergent adverse events (TEAEs) are defined as AEs reported on or after the first day of enrollment in this long term safety study.

All information pertaining to an AE noted during the study will be listed by subject, detailing verbatim term given by the PI or designee, preferred term, system organ class (SOC), onset date, resolution date, severity, seriousness, action taken, outcome, and drug relatedness. The event onset will also be shown relative (in number of days) to date of first dose in this study.

Treatment-emergent AEs will be summarized by the number of subjects reporting a TEAE, SOC, preferred term, severity, relationship to study drug (causality), and seriousness. When summarizing AEs by severity and relationship, each subject will be counted only once within a system organ class or a preferred term by using the event with the highest severity and greatest relationship within each classification.

Adverse events will also be summarized by windows of exposure to study drug. The windows will include but are not limited to: 1) within the first 24 hours of exposure, 2) up to 1 month of exposure, 3) up to 3 months of exposure, 4) up to 6 months of exposure and 5) up to 12 months of exposure.

AEs will also be summarized based on extent of exposure as described in Section 7.7

Serious AEs will be summarized by severity, and relationship to study drug, and individual SAEs will be listed by subject. In addition, a list of subjects who prematurely discontinue from the study due to an AE will be provided.

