7.7 EXTENT OF EXPOSURE

Extent of exposure will be based on days of treatment and the body surface area treated (face, upper back, and/or upper chest/shoulders) as collected at each visit for each subject. AEs will also be summarized by extent of exposure to determine if there is a safety signal due to duration of exposure or total body area exposed.

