#### 4.5 Safety

#### 4.5.1 Adverse Events

All AEs that occur during the study or continue after enrollment into this study will be recorded and classified on the basis of Medical Dictionary for Regulatory Activities (MedDRA) terminology version 18.1. Adverse events ongoing at end of the pivotal study will be carried forward to this study, will not be considered treatment-emergent for this study, and will be summarized separately by SOC, PT, and relatedness. Treatment-emergent AEs (TEAEs) will be defined as AEs reported on or after the first day of enrollment in this long term safety study.

All information pertaining to an AE noted during the study will be listed by subject, detailing verbatim term given by the Investigator or designee, preferred term, system organ class (SOC), onset date, resolution date, severity, seriousness, action taken, outcome, and drug relatedness. The event onset will also be shown relative (in number of days) to date of first dose in this study.

Treatment-emergent AEs will be summarized by the number of subjects reporting a TEAE, SOC, preferred term, severity, relationship to study drug (causality), and seriousness. When summarizing AEs by severity and relationship, each subject will be counted only once, within a system organ class or a preferred term, by using the event with the highest severity and greatest relationship within each classification.

Serious AEs will be summarized by severity, and relationship to study drug, and individual SAEs will be listed by subject. In addition, a list of subjects who prematurely discontinue study drug due to an AE, had AEs leading to treatment modification, and AEs that resulted in death will be provided.

Adverse events will also be summarized by windows of duration of exposure to study drug to determine if there is a safety signal due to duration of exposure. The windows of exposure will include but are not limited to: 1) within the first 24 hours (i.e. Day 1 of the LTS study), 2) up to 1 month (i.e. 2-30 days), 3) up to 3 months (i.e. 31-90 days), 4) up to 6 months (i.e. 91-180 days) and 5) up to 12 months (i.e. 181-365 days).

Adverse event incidence will also be summarized by the extent of exposure categories (in grams) as described in section 4.4.

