Treatment Emergent Adverse Events (TEAE) by System Organ Class, Preferred Term, and Duration of Exposure Safety Population

System Organ Class Preferred Term	Within 24 hours (N=XXX)	Within 2-30 days (N=XXX)	Within 31-90 Days (N=XXX)	Within 91-180 Days (N=XXX)	Within 181-365 Days (N=XXX)	Overall (N=XXX)
Number of Subjects with at Least One TEAE Number of Events	xx (xx.x)	xx (xx.x)	xx (xx.x)	xx (xx.x)	xx (xx.x)	xx (xx.x) xx
System Organ Class 1	xx (xx.x)	xx (xx.x)	xx (xx.x)	xx (xx.x)	xx (xx.x)	xx (xx.x)
Preferred Term 1	xx (xx.x)	xx (xx.x)	xx (xx.x)	xx (xx.x)	xx (xx.x)	xx (xx.x)
Preferred Term 2	xx (xx.x)	xx (xx.x)	xx (xx.x)	xx (xx.x)	xx (xx.x)	xx (xx.x)
System Organ Class 2	xx (xx.x)	xx (xx.x)	xx (xx.x)	xx (xx.x)	xx (xx.x)	xx (xx.x)
Preferred Term 1	xx (xx.x)	xx (xx.x)	xx (xx.x)	xx (xx.x)	xx (xx.x)	xx (xx.x)
Preferred Term 2	xx (xx.x)	xx (xx.x)	xx (xx.x)	xx (xx.x)	xx (xx.x)	xx (xx.x)

Note(s): Adverse event terms were coded using MedDRA dictionary version 18.1. Subjects are counted once within each level of summary. Duration of exposure is based on date of first dose of SB204, which could be in the previous study (NI-AC301 or NI-AC302).

Source: Listing xx.x.x.x, Program: xxxxx.sas, Output: T xx.x x x xxxx.rtf, Generated on: DDMMMYYYY HH:MM

Programmer Note: Order SOC by decreasing frequency and preferred term by decreasing frequency within SOC based on overall incidence.

Protocol Number: NI-AC303

Table 14.3.3.2.2

Treatment Emergent Adverse Events (TEAE) by System Organ Class, Preferred Term, and Extent of Exposure Safety Population

System Organ Class Preferred Term	1-100 grams (N=XXX)	>100-330 grams (N=XXX)	>330-675 grams (N=XXX)	>675 Grams (N=XXX)	Overall (N=XXX)
Number of Subjects with at Least One Event	xx (xx.x)	xx (xx.x)	xx (xx.x)	xx (xx.x)	xx (xx.x)
Number of Events	xx	xx	xx	xx	xx
System Organ Class 1 Preferred Term 1 Preferred Term 2	xx (xx.x)	xx (xx.x)	xx (xx.x)	xx (xx.x)	xx (xx.x)
	xx (xx.x)	xx (xx.x)	xx (xx.x)	xx (xx.x)	xx (xx.x)
	xx (xx.x)	xx (xx.x)	xx (xx.x)	xx (xx.x)	xx (xx.x)
System Organ Class 2 Preferred Term 1 Preferred Term 2	xx (xx.x)	xx (xx.x)	xx (xx.x)	xx (xx.x)	xx (xx.x)
	xx (xx.x)	xx (xx.x)	xx (xx.x)	xx (xx.x)	xx (xx.x)
	xx (xx.x)	xx (xx.x)	xx (xx.x)	xx (xx.x)	xx (xx.x)

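### The AE-by-duration tables report crude percentages over windows of unequal observable time, so they can show a rise with exposure when risk is constant; add rates per subject-time at risk.

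*SAP*

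**What the plan says.** SAP 4.5.1 gives the analysis a purpose: adverse events are to be "summarized by windows of duration of exposure to study drug to determine if there is a safety signal due to duration of exposure". Protocol 7.7 states a similar aim for the extent-of-exposure summaries, "to determine if there is a safety signal due to duration of exposure or total body area exposed".

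The SAP windows are "1) within the first 24 hours (i.e. Day 1 of the LTS study), 2) up to 1 month (i.e. 2-30 days"), then "3) up to 3 months (i.e. 31-90 days), 4) up to 6 months (i.e. 91-180 days"), then "5) up to 12 months (i.e. 181-365 days"). The day ranges do not overlap. Protocol 7.5.1 lists the same windows without day ranges, ending "4) up to 6 months of exposure and 5) up to 12 months of exposure".

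SAP 4.1 summarises categorical data by counts and percentages of N. The shell for Table 14.3.3.2.1 follows this: its first row is "Number of Subjects with at Least One TEAE", each window has a count, a percentage and an undefined N, and no row holds time at risk. The same shell serves every by-duration AE table through 14.3.3.11.1. Its footnote starts the duration clock at the first SB204 dose, which may lie in the pivotal study. The footnotes to the TEAE overview and Table 14.3.3.2.2 start TEAE onset at the beginning of treatment in this study. Neither document plans an event rate per subject-time, a hazard or a time-to-onset estimate for adverse events.

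**The concern.** The chance of at least one event in a window grows with the time for which a subject can be observed in it. When observable time differs between columns, crude percentages differ even if the underlying risk does not. The study has a single open-label arm, so no control column shares the same windows and lets the effect cancel.

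Long-term safety is the primary objective, and this is the only planned AE analysis by time on drug. A reader who uses the table as the SAP proposes could report a duration signal that is an artefact of window length, miss a real fall in risk, or be unable to separate a real late increase from the effect of width.

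**Working it through.** **Inputs from the documents.** Window widths from SAP 4.5.1 (end − start + 1): 1, 29, 60, 90 and 185 days. Treatment in this study lasts up to 280 days (Protocol 3.4). Pivotal treatment lasted 12 weeks, or 84 days (Protocol 3.7.2). The gap between studies is 0 to 7 days (Protocol 3.5).

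**Assumptions.** The documents give no AE rate, dropout or Experienced share. The main example uses a constant 1 event per subject-year, 50% Experienced, no gap, no dropout and all treated subjects as denominator. A subject may count once in each window.

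**Observable TEAE days.** On the shell's clock, Naïve subjects cover exposure days 1–280, so the last window holds 280 − 180 = 100 days. Experienced subjects cover days 84 + 1 = 85 to 84 + 280 = 364. That gives 0, 0, 6 (days 85–90), 90 and 184 (days 181–364). With a 7-day gap it is 0/0/0/89/185.

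**Constant risk.** The expected percentage is 1 − exp(−rate × days / 365.25). For example, 100 days gives 1 − exp(−0.274) = 24.0%, and 184 days gives 1 − exp(−0.504) = 39.6%. Their average is 31.8%.

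| Window (days) | Naïve | Experienced | Pooled 50:50 |
|---|---|---|---|
| 1 | 0.3% | 0% | 0.1% |
| 2–30 | 7.6% | 0% | 3.8% |
| 31–90 | 15.1% | 1.6% | 8.4% |
| 91–180 | 21.8% | 21.8% | 21.8% |
| 181–365 | 24.0% | 39.6% | 31.8% |

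At 0.25 per subject-year the pooled columns are 0.03%, 1.0%, 2.2%, 6.0% and 9.2%.

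**Rate halved after day 90 (1.0 to 0.5 per year).** For days 31–90, 91–180 and 181–365:

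- Pooled: 8.4%, 11.6%, 17.5%, a rise although risk fell.
- Naïve alone: 15.1%, 11.6%, 12.8%, lower in both later windows.

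**Sensitivity under constant risk.** The pooled case was repeated with 280-day risks of 5%, 30%, 50% and 80%, dropout of 0%, 30% and 50%, and 50% or 67% Experienced.

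- With an all-treated denominator, every scenario rises through all five windows. At 30% risk, 30% dropout and 50% Experienced the columns are 0.06%, 1.8%, 3.8%, 9.7% and 12.8%.
- With only subjects at risk in the window as denominator, all rise overall. At 67% Experienced the third window dips below the second (3.6% then 3.0% at 30% risk, no dropout).
- In Naïve subjects alone the last column can slip below the one before: 9.1% then 8.9% at 30% risk with 30% dropout and an all-treated denominator, or 9.7% then 9.5% at 30% risk if only a subject's first event is counted.

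**Rates.** At 1 per subject-year, subjects with an event divided by time up to that event (or the end of the window) give 100 / 12 = 8.3 per 100 subject-months in every window. If time is not stopped at the event, the pooled values drift down with width: 8.3, 8.0, 7.7, 7.4 and 6.8.

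**The case against.** The strongest reply is that the analysis is descriptive, untested and unpowered, that the day ranges are printed in the column headings, and that the SAP does not limit itself to the listed windows. The AE listing (16.2.8.1) carries start dates and duration of exposure, so rates could be derived later. All of that is true. But the SAP says these tables are meant to find a duration signal, and nothing prespecifies the rates that would serve that purpose.

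Several stronger readings are tempting and do not hold:

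- A reader might infer that nothing else is examined over time. Tolerability scores and vital signs are summarised by visit, without any window-width effect, and they cover the local reactions and blood pressure discussed in Protocol 1.5. TEAEs are also shown by prior treatment and by grams, although grams mix time with area treated. The gap concerns adverse events by time on drug.
- A reader might apply the nominal widths and expect columns from 0.3% to 39.7% at 1 per subject-year. No subject has 1/29/60/90/185 observable TEAE days, so that gradient cannot arise.
- A reader might infer that the table always rises, or always hides a fall. The Naïve-only results above show otherwise.
- A reader might take the protocol's windows as cumulative. The SAP's day ranges and the shell headings are already disjoint; only the SAP's labels lag behind.

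**Conclusion.** The point stands as a defect of the planned by-duration AE tables that should be corrected. Their percentages follow observable time, denominator and dropout as well as risk. In the main example, constant risk gives pooled columns from about 0.1% to 31.8%, and a halving of risk after day 90 still gives a pooled rise from 8.4% to 17.5%. These sizes rest on the assumed event rate, the 50% Experienced share, full follow-up and the shell's clock. Part of the pooled gradient comes from the two clocks: Experienced subjects can have almost no TEAE before exposure day 85, yet stay in an all-treated denominator.

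The direction of the trend is not fixed, so the documents do not support saying that a false rise is certain. Nor is the duration question beyond the data. The planned tables cannot answer it reliably; rates from the collected dates could address it.

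**What to change.** In SAP 4.5.1 and in Tables 14.3.3.2.1 and 14.3.3.3.1, at least for the overall and SOC rows, add for each window:

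- the number of subjects at risk;
- the subject-time at risk;
- subjects with an event in that window per 100 subject-months, with a 95% CI.

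Count time at risk only from the start of this study, when a TEAE can be recorded, and stop it at the subject's first event in the window. Experienced subjects' pivotal-study days must be left out; including them would deflate the early rates and create a new false rise. Show the rates for Experienced, Naïve and overall.

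State that the duration question is read from these rates and keep the counts and percentages as supportive. Align the SAP's up-to labels with the disjoint day ranges. Also reconcile the first window, which SAP 4.5.1 ties to Day 1 of this study while the shell footnote counts from the first SB204 dose. Rates are not needed in the death tables or other sparse tables.

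The cost is SAP and shell wording plus one derivation from dates already collected. The downside is wider tables, and unstable rates for rare terms and in the 1-day window, where 300 Naïve subjects (half of 600) would supply only 300 subject-days.

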3.4 DOSAGE/DOSE REGIMEN

SB204 will be dispensed from a dual-chamber pump designed to deliver approximately equal amounts of NVN1000 Gel and hydrogel. NVN1000 Gel will be opaque and the hydrogel will be clear. The subject will instantly mix the two substances in the palm of the hand and then immediately massage a thin layer over the acne affected areas once daily after washing. The product should be mixed for about 5 seconds until thoroughly combined with a uniform opaque appearance then applied with the fingertips. Subjects should apply SB204 prior to bedtime.

Up to 2.7 g of SB204 4% will be applied evenly over the acne affected area, including the face, chest, back, and upper shoulders once a day for a period of up to 40 weeks (280 days). The amount of SB204 per application will vary depending on the areas to be treated as shown in Table 1 below. One pump stroke (0.9 g) will be used for the face. Application to the face, upper back and upper chest/shoulders will require up to 2.7 g (three (3) pump strokes).

Table 1: Dosing Amount by Area

Area (BSA)	Number of Pump Strokes	Amount of Product	
Face (3%)	1	0.9 g	
Upper Back (6%)	1	0.9 g	
Upper Chest/Shoulders (8%)	1	0.9 g	

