4. STUDY PROCEDURES AND METHODS

4.1 SUBJECT ENTRY PROCEDURES

Prospective subjects as defined by the eligibility criteria in Sections 3.7.2 and 3.7.3 (Inclusion/Exclusion Criteria) will be considered for entry into this study. Subjects' informed consent/assent must be obtained prior to conducting any procedures for this study and after completion of the Week 12 assessments for NI-AC301 or NI-AC302.

Some baseline procedures (i.e., review of inclusion/exclusion criteria, brief physical exam, blood pressure and pulse rate, lesion counts, cutaneous tolerability, adverse event assessment, concomitant medication review and UPT) must be completed prior to dispensing open label study medication.

WOCBP having a positive UPT at baseline may not be randomized into the study. Women of childbearing potential must agree to use an effective form of contraception during participation in the study and for 30 days after their final study visit. Effective contraception is defined as stabilized on oral contraceptive for at least three months (90 days), intrauterine device (IUD), condom with spermicide, diaphragm with spermicide, implant, NuvaRing®, medroxyprogesterone injection, transdermal patch or abstinence with a documented second acceptable method of birth control should the subject become sexually active. Females taking hormonal contraceptives must have taken the same type for at least three months (90 days) prior to entering the study and must not change type during the study. Subjects who had used hormonal contraception and stopped must have stopped no less than three months prior to the start of the study.

A female is considered to be of childbearing potential UNLESS she is post-menopausal (no menses for 24 consecutive months), surgically sterilized, or without a uterus and/or both ovaries. Premenarchal girls are considered to be of childbearing potential.

After the required procedures are completed and study eligibility is confirmed, study drug will be dispensed to the subject. The subject will be trained on the mixing, application, and storage of the study drug. All study drug applications will be done at home.

Table 2: Schedule of Visits and Procedures

Study visits should occur at approximately the same time of day throughout the study.

PROCEDURES	Visit 1 ¹ Baseline (Day 0)	Visit 2 ³ Week 4 ±5 days (Day 28)	Visit 3 Week 12 ±7 days (Day 84)	Visit 4 Week 24 ±7 days (Day 168)	Visit 5 Week 36 ±7 days (Day 252)	Visit 6 ⁴ Week 40/ET ±7 days (Day 280)

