### 4.4 Extent and Duration of Exposure

Summaries of the duration of exposure, days of exposure, and extent of exposure (calculated total grams) to study drug will be presented, overall and by whether previously randomized to SB204 (SB204 experienced) or randomized to Vehicle (SB204 naïve). This information plus study drug management details will be listed as well. All exposure endpoints will take into account whether the subject received SB204 in the previous study (NI-AC301 or NI-AC302).

Duration of exposure will be defined as:

Date of Last Drug Administration – Date of First Drug Administration + 1 day

Where date of first drug administration is the date of first treatment in the previous pivotal study for subjects randomized to SB204 in the previous study, and date of first dose in the LTS for subjects randomized to vehicle in the previous study.

Days of exposure will be defined as the total number of days that the subject reported taking study medication, and includes the days of exposure to SB204 in the previous study (NI-AC301 or NI-AC302) if applicable.

Extent of exposure will be based on the number of areas treated (face, upper back, and/or upper chest/shoulders, and any other areas reported) and the number of days with treatment. For subjects randomized to SB204 in the previous studies, drug was only applied to the face so for the days of exposure from the previous studies, it will be assumed that there is only one area of application, i.e. the face.

Each application is equal to 0.9 g. Extent of exposure is estimated as the sum of application areas (face only=1, face and chest=2, etc.) times the number of days of application to those areas times 0.9g. For example, a subject who applies 200 applications to the face only will have extent of exposure = 180g, while a subject who applies 100 applications to the face and 50 applications to the upper back will have extent of exposure = 135 g. The maximum extent of exposure would be: [0.9 grams x number of days on treatment in previous study] + [0.9 grams x 4 areas x number of LTS days on treatment]. Most subjects will have less exposure than this, so extent of exposure will be categorized logically depending on actual distribution of subjects. Initially, quartiles will considered.

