Source: Listing xx.x.x.x, Program: xxxxx.sas, Output: T\_xx.x\_x\_xxxx.rtf, Generated on: DDMMMYYYY HH:MM

Protocol Number: NI-AC303

Using shell 14.3.2.1, Repeat table for the following:

Table 14.3.2.2 Shift from Baseline in Cutaneous Tolerability Evaluation - Scaling - Summarized Continuously by Study Visit Safety Population

Table 14.3.2.3 Shift from Baseline in Cutaneous Tolerability Evaluation - Dryness - Summarized Continuously by Study Visit Safety Population

Table 14.3.2.4 Shift from Baseline in Cutaneous Tolerability Evaluation - Pruritus - Summarized Continuously by Study Visit Safety Population

Table 14.3.2.5 Shift from Baseline in Cutaneous Tolerability Evaluation - Burning/Stinging - Summarized Continuously by Study Visit Safety Population

Protocol Number: NI-AC303

Table 14.3.3.1

Treatment Emergent Adverse Events (TEAE) Overview
Safety Population

Number of Subjects with	SB204 Experienced (N=XXX)	SB204 Naïve (N=XXX)	Overall (N=XXX)
Any TEAE	xx (xx.x)	xx (xx.x)	xx (xx.x)
Number of TEAEs	xx	xx	
Treatment-Related TEAE Number of Treatment-Related TEAEs	xx (xx.x)	xx (xx.x)	xx (xx.x)
	xx	xx	xx
TEAE Leading to Treatment Modification	xx (xx.x)	xx (xx.x)	xx (xx.x)
Number of TEAE Leading to Treatment Modification	xx	xx	xx
Treatment-Related TEAE Leading to Treatment Modification Number of TRTEAE Leading to Treatment Modification	xx (xx.x)	xx (xx.x)	xx (xx.x)
	xx	xx	xx
TEAE Leading to Treatment Discontinuation	xx (xx.x)	xx (xx.x)	xx (xx.x)
Number of TEAE Leading to Treatment Discontinuation	xx	xx	xx
Treatment-Related TEAE Leading to Treatment Discontinuation Number of TRTEAE Leading to Treatment Discontinuation	xx (xx.x)	xx (xx.x)	xx (xx.x)
	xx	xx	xx
Serious TEAE	xx (xx.x)	xx (xx.x)	xx (xx.x)
Number of Serious TEAEs	xx	xx	xx
Treatment-Related Serious TEAE	xx (xx.x)	xx (xx.x)	xx (xx.x)
Number of Treatment-Related Serious TEAEs	xx	xx	xx
TEAE Leading to Death	xx (xx.x)	xx (xx.x)	xx (xx.x)
Number of TEAE Leading to Death	xx	xx	xx
Treatment-Related TEAE Leading to Death	xx (xx.x)	xx (xx.x)	xx (xx.x)
Number of Treatment-Related TEAE Leading to Death	xx	xx	

Note: TEAE onset is based on the start of treatment in the LTS. Adverse events were coded using MedDRA 18.1. TR=Treatment-Related.

Source: Listing xx.x.x.x, Program: xxxxx.sas, Output: T\_xx.x\_x\_x\_x\_xxx.rtf, Generated on: DDMMMYYYY HH:MM

Protocol Number: NI-AC303

Table 14.3.3.2.1

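### SAP 4.5.1 codes the first-24-hours AE window as Day 1; with bedtime dosing, overnight and next-day onsets fall in the 2-30 day column

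*SAP*

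**What the plan says.** **Windows.** Protocol 7.5.1 lists windows of exposure that begin "1) within the first 24 hours of exposure, 2) up to 1 month of exposure". SAP 4.5.1 turns the first two into "1) within the first 24 hours (i.e. Day 1 of the LTS study), 2) up to 1 month (i.e. 2-30 days". Shell 14.3.3.2.1 heads its first column as within 24 hours and its second as 2-30 days. The same layout is reused for the nine other duration tables, 14.3.3.3.1 to 14.3.3.11.1.

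**Dosing time and place.** Protocol 3.4: "Subjects should apply SB204 prior to bedtime". Protocol 4.1: "All study drug applications will be done at home". No clock time is given.

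**Start of treatment emergence.** SAP 4.5.1: "Treatment-emergent AEs (TEAEs) will be defined as AEs reported on or after the first day of enrollment in this long term safety study". Protocol 7.5.1 has the same rule. The note to Table 14.3.3.1 says instead "TEAE onset is based on the start of treatment in the LTS", and the notes to Tables 14.3.3.2.2 and 14.3.3.13 repeat it.

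**Onset data.** SAP 4.5.1: "The event onset will also be shown relative (in number of days) to date of first dose in this study". Protocol 4.3.1 and Listing 16.2.8.1 call for onset dates; neither mentions an onset time.

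**Day numbering.** SAP 4.4 defines duration of exposure as "Date of Last Drug Administration – Date of First Drug Administration + 1 day", which makes the first-dose date day 1. The schedule in SAP 3.3 labels Baseline Day 0. Listing notes count days from the first dose (16.2.2) or from the first day of the LTS (16.2.4.3, 16.2.5, 16.2.7.4). The note to Table 14.3.3.2.1 measures duration from the first SB204 dose ever, which may lie in the pivotal study.

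**The concern.** A calendar day stands in for 24 hours of exposure only if dosing happens early on that day. Here the first dose is applied at home in the evening, after a clinic visit. A headache that starts overnight or the next morning is within 24 hours of the first dose, but it is dated Day 2 and counted under 2-30 days.

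The column can also take in events that precede exposure. Protocol 4.1.1 collects AEs at the Baseline visit from consent onward, before any home application, and SAP 4.5.1 makes such events treatment-emergent.

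Safety is the only stated objective, and ten tables would carry the column. A reader would take its heading at face value, and because the documents call for onset dates only, a true 24-hour window could not be rebuilt after lock.

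**Working it through.** The documents give no figure to reproduce, so the check is hour arithmetic. The clock times are assumptions.

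**Step 1: Day 1 = date of first application (the SAP 4.4 convention).** For a dose at clock hour d, the post-dose hours left on Day 1 are 24 − d, and the share of the first 24 post-dose hours that falls on Day 2 is d/24.

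| Assumed dose | Hours on Day 1 | Share on Day 1 | Share in 2-30 days |
|---|---|---|---|
| 20:00 | 24 − 20 = 4 | 4/24 = 17% | 83% |
| 22:00 | 24 − 22 = 2 | 2/24 = 8% | 92% |
| 23:00 | 24 − 23 = 1 | 1/24 = 4% | 96% |

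More than half falls on Day 2 whenever d/24 > 1/2, that is, for any dose between noon and midnight. A first dose just after midnight reverses this: at 00:30, Day 1 holds 23.5 of 24 hours (98%).

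**Step 2: pre-dose time in the column under the SAP text.** If consent (hour c) and first application fall on the same date, the pre-dose share of AE-collection time on that day is (d − c)/(24 − c). For a 22:00 dose:
- consent at 09:00: 13/15 = 87%
- consent at 17:00: 5/7 = 71%

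**Step 3: other readings of Day 1.**
- If Baseline is Day 0 with the first dose that evening, Day 1 is the next calendar day. For a 22:00 dose it covers post-dose hours 2 to 26, so it holds 22 of the first 24 hours (92%). The direction reverses, but onsets in the first two hours, on Day 0, then have no window.
- If Day 1 is the enrolment date and first use is delayed, Day 1 may contain no exposure at all.

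**Step 4: who enters the column.** The SAP text anchors it to the LTS, so all subjects can enter. The note to Table 14.3.3.2.1 anchors it to the first SB204 dose ever. An SB204-experienced subject whose first pivotal dose was 84 days earlier starts the LTS on exposure day 84 + 1 = 85 (31-90 column). With a further 7-day gap it is day 92 (91-180 column). Under that anchor only SB204-naive subjects can have an LTS event in the first column.

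**Step 5: which events move.** Protocol 1.5 describes the known erythema as lasting about 5-10 minutes and starting shortly after application. After a dose at 20:00-23:00 it still falls on Day 1. Protocol 4.2 makes erythema, scaling, dryness, pruritus and burning/stinging AEs only if severe or leading to discontinuation; otherwise they go to the tolerability tables, which these windows do not touch. What moves is overnight and next-day AEs. Headache and hypotension, the theoretical systemic risks in Protocol 1.5, are not subject to that restriction.

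**The case against.** A reader might infer from the 83-96% that the column would miss nearly all acute reactions to first application. The documents do not support that. The percentages count hours, and they would measure lost events only if onset were spread evenly over 24 hours. Protocol 1.5 says otherwise for the one reaction whose timing it describes, and most local signs never reach these tables. That limit stands in full.

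Other points on the plan's side:
- SAP 4.5.1 gives the purpose of the windows as finding a signal related to duration of exposure, and the list is open-ended. An acute first-application purpose for the column is an inference. The 24-hour label, however, comes from the protocol and the shell.
- Headache and hypotension are theoretical risks, and Protocol 1.5 reports no detectable systemic exposure to the parent compound. This lowers the expected number of misplaced events; it does not make the column correct.
- Day 1 is undefined, and one reading reverses the direction. This is right, and it is part of the defect: none of the readings examined delivers the first 24 hours after an evening dose.
- Listing 16.2.8.1 shows first-dose and AE start dates, so Day 2 events can be found subject by subject. True, but the summary tables stay mislabelled.
- Asking sites whether a first-day AE began before or after application would be a change to data collection. AEs are elicited at visits (Protocol 6.2), and the first post-dose visit is Week 4, so answers would lean on recall. That remedy is not recommended.

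**Conclusion.** The point holds as a descriptive misallocation. With Day 1 as the first-application date and an evening dose, the column labelled as 24 hours covers 1 to 4 of the first 24 post-dose hours for doses from 20:00 to 23:00, and overnight and next-day AEs are counted under 2-30 days. Immediate reactions are still captured. The number of events affected cannot be derived from the documents.

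Three gaps add to it: Day 1 is not defined against the Day 0 Baseline, the SAP text and shell notes start TEAEs at different points, and the text and shell anchor the window to different first doses. Under the shell's anchor the misallocation concerns SB204-naive subjects only.

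The size rests on assumed clock times and on the day-1 reading of SAP 4.4. The direction holds under that reading for any dose between noon and midnight. No test or sample size is affected, because the study is descriptive. The change is worth making because the plan, followed as written, yields a mislabelled column in ten safety tables.

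**What to change.** In SAP 4.5.1 and the 14.3.3.x.1 shells, using dates already collected:

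1. Define Day 1 as the date of first application, and state how it relates to the Day 0 Baseline. Use one anchor in text and shell notes, and say which subjects can enter the first column.
2. Make window 1 Days 1-2, relabelled as first application day and following day, and window 2 Days 3-30.
3. Start TEAEs at the first LTS application date in both text and shells. Record this and the new window as departures from Protocol 7.5.1. AEs between consent and first application remain in Listing 16.2.8.1.

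The cost is SAP and shell wording and some programming; no new data are needed. There are two downsides:
- Window 1 runs past 24 hours. Its post-dose length is (24 − d) + 24, which gives 28, 26 and 25 hours for doses at 20:00, 22:00 and 23:00, and more for earlier doses (32 hours at 16:00).
- Events on the first-application date but before the application cannot be fully separated by date alone. A table footnote should say so.
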